INTERACT

1

PROTOCOL SYNOPSIS

OBSERVATIONAL RETROSPECTIVE STUDY

Title: INTensive dosE tinzapaRin in hospitalized Covid-19 paTients

Short Title: **INTERACT**

Protocol Date: 14 June 2021

PROTOCOL SYNOPSIS

Study Title	INT ensive dos E tin zapa R in in hospit AL ized C ovid-19 pa T ients
--------------------	--

Study Rationale	A prothrombotic state, attributable to a cytokine storm induced by severe acute respiratory syndrome coronavirus 2 (SARS-Cov-2) and leading to activation of the coagulation cascade, is a recognized feature of Coronavirus disease 2019 (COVID-19) infection. This can manifest in venous thromboembolism (VTE) , arterial thrombosis events (ATE) and disseminated intravenous coagulation (DIC) and coagulopathy is reflective of more severe disease and adverse prognosis [1]. A significant number of patients with COVID-19 require single or multiple organ support on the Intensive Care Unit (ICU) , estimated to be between 12 and 17% of patients [2,3,4,5]. with the reported mortality in these cohorts between 25 and 40% [2, 6].
Introduction	
International guidelines recommend that hospitalized patients with COVID-19 should receive pharmacological prophylaxis against VTE, in the absence of contraindications [7,8,9]. With respect to how VTE prophylaxis is achieved, Low Molecular Weight Heparins (LMWH), in addition to their well-known anticoagulant properties, appear to have additional antiviral and anti-inflammatory effects that may be potentially beneficial in hospitalized COVID-19 patients. [10,11].
 
Though international and national guidelines states that all hospitalized patients with COVID-19 should receive pharmacologic thromboprophylaxis, the rising incidence of thrombotic complications in COVID-19 patients has led a lot of hospitals to adopt the strategy of increasing the dose of anticoagulation for prophylaxis to 'intermediate' or "therapeutic" doses using a risk-adapted strategy with increased doses administration based on factors associated with increased risk; clinicians weigh the benefits and risks of therapeutic anticoagulation in terms of thrombosis and major bleeding risk for individual patients.
 
Additionally, LMWHs have different physiochemical characteristics as a result of the diverse methods of their manufacturing. The variations in molecular composition and pharmacological properties of LMWHs are reflected in differences in their clinical efficacy and safety. Each LMWH should, therefore, be considered as a unique substance. Tinzaparin is the only LMWH known that is prepared by enzymatic hydrolysis with heparinase [12,13,14,15]. Due to its preparation method, tinzaparin has distinct properties than other LMWHs including and not limited to: higher Anti-IIa activity and Anti-Xa/Anti-IIa activity ratio, higher release of Tissue Factor Pathway Inhibitor (TFPI), less dependence from renal function for its clearance and more complete neutralization from its antidote, if needed. Due to the key role of increased Thrombin generation (IIa) and Tissue factor (TF) pathway activation in COVID-19-associated thrombosis [16], special properties of tinzaparin in Anti-IIa activity and TFPI production and release from endothelial cells, as well as significant effects of TFPI in various vascular, inflammatory, cardiovascular, hematological and oncological disorders [17,18,19,20,21], tinzaparin could have an expanded role beyond its well-known anticoagulant function.
 
The purpose of this study is to evaluate the overall clinical effectiveness and safety of 'intermediate' or "therapeutic" doses anticoagulation with tinzaparin administered for thromboprophylaxis in COVID-19 patients with moderate disease severity during hospitalization in Greek hospitals.


Study Objectives

Primary Objectives

The **primary objective** of this study is to evaluate the current management approach with “intermediate” or “therapeutic” doses of tinzaparin for thromboprophylaxis in hospitalized patients, non on ICU organ support, with confirmed COVID-19.

- Evaluate incidence of thrombotic events
- Evaluate incidence of bleeding events

Secondary Objectives

The **secondary objective** is to

- ✓ Examine the course of illness of COVID-19 via measure of clinical improvement and/or survival, assessed at pre-specified time points post admission

Patients demographic & somatometric data, medical history (thrombosis & bleedings related history, co-morbidities, chronic use of medications, results of laboratory tests etc.), clinical parameters, anticoagulant prophylaxis dose & duration, efficacy (thrombosis events), safety (bleedings), imaging and laboratory tests results and information about other supportive treatment will be recorded; more than one outcomes could be recorded.

Based on analysis of collected data, **we'll examine correlations between thromboprophylaxis approach, patients' profiles and clinical outcomes.**

Study Endpoints

Primary Endpoints

- **Incidence of thrombotic events** (total & per type e.g. PE, DVT, symptomatic, incidental, proximal, distant etc.)
- **Incidence of bleeding events** (total & per type e.g. Major, CRNMB and minor)

Secondary Endpoint

- **World Health Organization (WHO) progression scale** (range from 0 (healthy) to 10 (death); values below or equal to 5 correspond to the absence of any oxygen supply beside nasal or facial mask)
- **Length of hospital stay (days)**

Study Design

This is a retrospective phase IV, observational, non-interventional cohort study that aims to collect data regarding thromboprophylaxis management in high thrombotic risk hospitalized, non on ICU, patients with COVID-19 pneumonia. Specifically, we will collect retrospectively data for patients received thromboprophylaxis with tinzaparin, according to current clinical practice, during hospitalization, for one year before the study initiation date, to evaluate safety and efficacy of thromboprophylaxis and to examine possible associations of

patients' profiles with thrombotic and bleeding events and the course of illness in this cohort of patients.

We will collect data retrospectively in paper CRFs, recorded from the treating physicians.

Additionally, we will assess the association of a panel of laboratory and clinical parameters representing an inflammatory and hemostatic state with VTE and bleeding events and clinical outcomes.

Institutional Review Board will approve the study.

Basic/common markers/parameters

- ✓ *D-Dimers*
- ✓ *C-reactive protein (CRP)*
- ✓ *hemoglobin*
- ✓ *platelets count*
- ✓ *ferritin*
- ✓ *fibrinogen*
- ✓ *SpO₂ in FiO₂ 21%*

In all cases, laboratory and clinical parameters will be collected at 3 time points: at admission/baseline, after one week and at discharge.

Subject Population

Key criteria for Inclusion and Exclusion

Inclusion Criteria

1. Patients admitted to hospital with COVID-19, PCR+ SARS-CoV-2 infection (from any specimen) administered thromboprophylaxis with tinzaparin in intermediate or therapeutic dose
2. Age \geq 18 years
3. Signed informed consent

Exclusion Criteria

1. Patients admitted to ICU with COVID-19, PCR+ SARS-CoV-2 infection (from any specimen)
 2. Age < 18 years
 3. Pregnancy
 4. Current diagnosis or suspicion of pulmonary thromboembolism or deep vein thrombosis
 5. Progression to death was imminent and inevitable within 24 hours from the admission, irrespective of the provision of treatments
 6. Not signed informed consent
-

Study Phases**Screening**

(1) Screening: screening patient files for eligibility, obtaining consent, If eligible

All the data will be gathered from medical records by chart review of the individual patients in a retrospective fashion. There will no direct patient interaction in the study.

Data collection

- Demographic data collection (Gender, Date of birth, Weight, Height, etc.)
- Medical history & pathologic features (Thrombosis & bleedings related history, risk factors, recent surgery, co-morbidities, chronic use of medications, results of laboratory tests, clinical parameters etc.)
- Anti-coagulant administration data
- Thrombotic & bleeding events during course of hospitalization
- Other adverse events related to anticoagulation
- Clinical improvement and/or survival during hospitalization

Timepoints of evaluation

Data of Covid-19 pneumonia patients retrospectively enrolled in the study will be evaluated on a regular basis following the Baseline Visit;

Visit 1 – Baseline, at admission;

Visit 2 - will be after 1 week \pm 2 days

Visit 3 - will be by at discharge from hospital

Statistical analysis & report**Statistical analysis****Statistical and Analytic Plan**

Descriptional statistical analysis will be performed for all study data along with epidemiology methods. Categorical data will be analyzed using the *chi-square* and *Fisher exact test*. Continuous variables will be reported as mean and standard deviations (SD) and will be analyzed using the *t-test* analysis. An unadjusted odds ratio (OR) will be calculated using a *Cochran-Mantel-Haenszel test*. To determine the impact of potential effect modifiers a *logistic regression model* will be used to calculate the adjusted odds ratio. For more complex correlations (i.e. inferential statistics) we will use, among other methods, *chi-square* or *Fisher exact tests*, *ANOVA*, *Mann-Whitney U tests* and *t-tests*, according to the data properties and in order to evaluate the relationships between different patient and disease characteristics with the primary and secondary study outcomes, such as:

- ✓ *Number of patients enrolled*
- ✓ *Co-morbidities*
- ✓ *Thrombosis risk factors*
- ✓ *Laboratory parameters*
- ✓ *Clinical parameters*
- ✓ *Type and duration of thromboprophylaxis therapy*
- ✓ *Therapy outcomes*
- ✓ *Thromboprophylaxis related complications*

and to present them, accordingly.

Due to the fact that this is an observational study the results of all correlations will be carefully discussed and will be used only to assess hypotheses.

Finally and depending on the collected data multivariate analysis may be performed in order to reveal confounding factors.

Clinical Study Report (CSR)

Analyzed parameters will be presented with standards statistical measures (mean values, median values, ranges, quartiles, percentages etc.) and the results will be presented accordingly into tables and informative plots.

A p-value of less than 0.05 will be considered statistically significant and all values will be reported with a 95% confidence interval (CI).

Study Registration

Study will be registered in

NIH, U.S. National Library of Medicine, Clinical Trials database of privately and publicly funded clinical studies, <https://clinicaltrials.gov/ct2/home>

Efficacy Evaluations

- ***Symptomatic/Suspected vein thromboembolism, including pulmonary embolism and deep vein thrombosis***

Confirmation of symptomatic PE requires symptoms of PE and one of the following findings

1. *A (new) intraluminal filling defect in (sub) segmental or more proximal branches on spiral CT scan or on MRI scan;*
2. *A (new) intraluminal filling defect or an extension of an existing defect or a new sudden cut-off of vessels on the pulmonary angiogram;*
3. *An inconclusive lung scan accompanied by documentation of (new) DVT in the lower extremities e.g., by compression ultrasound or venography.*

Confirmation of symptomatic DVT requires symptoms of DVT and:

1. *A (new) non-compressible venous segment on ultrasonography
Incidental PE with one of the following:*
2. *A (new) intra-luminal filling defect on CT scan, MRI scan, or pulmonary angiogram;*
3. *An inconclusive lung scan accompanied by documentation of (new) DVT in the lower extremities e.g., by compression ultrasound or venography.*

Fatal PE is:

1. *PE based on objective diagnostic testing or autopsy or*
-

-
2. *Death not attributed to a documented cause and for which DVT/PE cannot be ruled out*

Incidental DVT with the following finding:

Confirmation of incidental DVT requires inconclusive or no- symptoms of DVT and:

1. *A (new) non-compressible venous segment on ultrasonography*

**Safety Evaluations
(with regards to
anticoagulation)**

- **Major, Clinically Relevant Non-Major Bleeding (CRNMB), and minor bleeding**

Major bleeding will be defined as overt bleeding associated with: a fall in hemoglobin of 2 g/dL or more, or leading to a transfusion, or bleeding that occurs in a critical site or contributing to death.

- **Bleeding in a critical area or organ such as:**

- ✓ *Retroperitoneal*
- ✓ *Intracranial*
- ✓ *Intraocular*
- ✓ *Intraspinal*
- ✓ *Intra-articular*
- ✓ *Pericardial*
- ✓ *Intramuscular with compartment syndrome*

- **A clinically overt bleeding event**

- ✓ *that is associated with a fall in hemoglobin of 2.0 g/dL (>1.24 mMol/L) or more, or*
- ✓ *leading to a transfusion of ≥ 2 units of packed red blood cells or whole blood*

- **Bleeding contributing to death**

- Other **clinically relevant non-major bleedings (CRNMB)** will be defined as overt bleeding not meeting the criteria for major bleeding but associated with medical intervention, unscheduled contact (visit or telephone call) with a physician, (temporary) cessation of study treatment, or associated with discomfort for the patient such as pain, or impairment of activities of daily life.
 - All other bleeding events will be classified as **minor**
-

- **World Health Organization (WHO) progression scale**

Patient State	Descriptor	Score
Uninfected	Uninfected; no viral RNA detected	0

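### Tinzaparin dose and duration are related to events in the same stay without limiting exposure to the time before the event, so the outcome can alter the exposure

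*Combined protocol and SAP*

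**What the plan says.** - **Comparison planned.** Study Objectives ends by announcing "correlations between thromboprophylaxis approach", patient profiles and clinical outcomes. The Statistical and Analytic Plan lists "Type and duration of thromboprophylaxis therapy" among the characteristics to be related to the primary and secondary outcomes.
- **Exposure recorded.** Study Objectives mentions "anticoagulant prophylaxis dose & duration"; the Data collection list has only "Anti-coagulant administration data". Inclusion criterion 1 requires that the patient was "administered thromboprophylaxis with tinzaparin in intermediate or therapeutic dose". No section says whether a patient's dose is the initial, highest, last or predominant one, how changes are handled, or that dosing after an event is left out.
- **Events.** Data collection covers "Thrombotic & bleeding events during course of hospitalization", which is the period in which the drug is given.
- **Bleeding definition.** One of the alternative criteria for clinically relevant non-major bleeding (CRNMB) is an association with "temporary) cessation of study treatment".
- **Exclusion 4.** "Current diagnosis or suspicion of pulmonary thromboembolism or deep vein thrombosis", with no time point.
- **Methods.** Tests on contingency tables, comparisons of means or ranks, and logistic regression for adjusted odds ratios, with significance at 0.05. No time-to-event or time-varying method is named. The section limits the correlations to assessing hypotheses.

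**The concern.** An association between exposure and outcome can be interpreted only if the exposure comes first. Here both are read from the chart of a completed stay, and the outcome can change the exposure in two ways.

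1. **Bleeding and duration.** The CRNMB definition foresees that a bleed may coincide with a stop of the drug. A stop shortens the duration of therapy, a factor that the plan names. Bleeding would then look linked to short treatment even if duration had no effect.
2. **Thrombosis and dose.** Therapeutic dose is a qualifying prophylaxis category, and it is also a dose level that a thrombosis during the stay may prompt. If the abstractor or analyst uses the highest or last dose, a patient who had a thrombosis on the intermediate dose is counted in the therapeutic group.

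The likely result is a published odds ratio that reflects the response to the event. Covariate adjustment does not repair an exposure measured after the outcome.

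**Working it through.** The documents give no sample size, event rate, dose split or length of stay, so there is no plan figure to reproduce. Every input below is an assumption, and every scenario has no true effect of exposure.

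**1. Duration and bleeding.** Assume stays L that follow a gamma distribution with shape 4 and scale 2.5 days (mean 10, variance 25) with a floor of 3 days, a constant bleeding hazard giving a 2% or 5% risk over 10 days, and a bleed that ends treatment.
- Rough check, ignoring the floor: E[L²] = 25 + 10² = 125. At a low hazard, the mean stay of patients who bleed is about E[L²]/E[L] = 125/10 = 12.5 days, and the bleed falls on average halfway, at about 6.25 days.
- Simulation of 400,000 stays: mean duration 6.1 days with a bleed against 9.9 to 10.0 days without. The stays of patients who bled averaged 12.4 to 12.5 days.
- So if bleeds stop the drug, duration looks protective. If they did not, it would look harmful (about 12.4 against 9.9 days), because a longer stay gives more time to bleed. Neither pattern says anything about the effect of duration.

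**2. Dose group and thrombosis.** Let s be the share starting on therapeutic dose, with equal risk in both groups, and q the fraction of intermediate-dose thromboses later classed as therapeutic. Then

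OR = [1 + q(1 − s)/s] / (1 − q), whatever the event rate.

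| q | s = 0.3 | s = 0.5 | s = 0.7 |
|---|---|---|---|
| 0 | 1.00 | 1.00 | 1.00 |
| 0.25 | 2.11 | 1.67 | 1.48 |
| 0.50 | 4.33 | 3.00 | 2.43 |

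Example: s = 0.5, q = 0.25 gives (1 + 0.25)/0.75 = 1.67.

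False-positive rate of Fisher's test at 0.05 (equal groups, total N 300 or 600, risk 2% or 5%, 3,000 runs per setting): 2.0% to 3.9% at q = 0, 3.4% to 23.4% at q = 0.25, and 13.5% to 76.0% at q = 0.50.

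**3. Small counts.** Take 4/150 thromboses in each group and move m intermediate-dose events. Each group keeps 146 event-free patients, so OR = (4 + m)/(4 − m).
- m = 1: 5/3 = 1.67, p = 0.72
- m = 2: 6/2 = 3.0, p = 0.28
- m = 3: 7/1 = 7.0, p = 0.067
- m = 4: 0/146 v 8/154, p = 0.0072

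The estimate shifts with every patient moved, but in this example significance at 0.05 is reached only when all four move.

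**4. A repair that fails.** It may seem natural to take the dose just before onset for patients with an event and the first dose for the rest. Assume 50% start on therapeutic dose and 10% to 30% of intermediate starters escalate before the event time. Patients with events are then 50% + 0.5 × (10% to 30%) = 55% to 65% therapeutic, against 50% of the others. The OR is 0.55/0.45 = 1.2 to 0.65/0.35 = 1.9 from the rule alone.

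**The case against.** - **The dose group is undefined, not wrongly defined.** A reader might infer that the plan fixes one dose per patient and that events will therefore shift dose groups. It does not say so. An analyst who used the starting dose would avoid the problem for dose, though not for duration. The document is a synopsis and no CRF is shown, so dose-change dates may already be captured. This stands: the dose group can change, but need not.
- **Bleeds and dose group.** A reader might infer that a bleed moves patients into the intermediate group. The CRNMB text speaks of cessation, not reduction, and a stop moves nobody between groups. A reduction would do so only under a last-dose or predominant-dose rule. The secure effect of a bleed is on duration.
- **Existing wording helps.** Inclusion 1 and the recorded exposure refer to prophylaxis, and treating a diagnosed thrombosis is not prophylaxis in plain language. This is a partial safeguard, but it is not a rule for dose changes during the stay.
- **Exclusion 4.** It could be read over the whole chart, which would remove the very events to be counted. That reading is strained: thrombosis is a primary endpoint, events are collected during the stay, and the event definitions ask for new findings. Admission or treatment start is the likelier reading, and it leaves treatment doses given later in the stay unaddressed.
- **Reach.** The correlations are declared exploratory. That tempers interpretation but does not remove the bias.

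**Conclusion.** The concern holds for the exploratory correlations of dose and duration with thrombosis and bleeding. Followed as written, the plan relates exposure that may postdate the event to that event, with methods that cannot separate the two.

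The clearest case is duration: about 6 days with a bleed against about 10 without, given an assumed mean stay of about 10 days and bleeds that end treatment. The dose effect is conditional on a highest-dose or last-dose rule. A true OR of 1 would then appear as 1.5 to 2.1 if a quarter of intermediate-dose thromboses are reclassified, and as 2.4 to 4.3 if half are. How often either happens cannot be learned from the documents.

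A reader might infer that the primary results are biased too. The documents do not support that: overall thrombosis and bleeding incidences are whole-cohort figures and do not depend on dose group.

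**What to change.** In the statistical section:

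1. Define exposure by one rule applied alike to patients with and without events: the dose at the first qualifying prophylactic administration. Use it for the main comparison.
2. Add a sensitivity analysis with time-varying dose, in which exposure and follow-up end at the first event.
3. State that doses given to treat a suspected or confirmed VTE do not count as thromboprophylaxis, for entry or for dose group.
4. Do not relate total duration to events unless it is cut off at the event and analysed as time-varying.

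In the eligibility criteria, state that exclusion 4 is assessed at the first qualifying dose, so that later events in the stay are kept.

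On the CRF, record dates of dose changes, stops and event onset, if these are not already there.

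The cost is a few sentences and a little more chart abstraction. It is lowest before the paper CRFs are completed, since adding dates later means going back to the charts. Two limits remain. A first-dose rule blurs contrasts when doses change later, which is why the time-varying analysis is needed. It also does not remove confounding from the risk-adapted dosing that the Introduction describes.

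### Marker and dose associations use a thrombotic outcome that includes incidental PE and DVT, with no use of who was scanned, so they are open to detection bias

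*Combined protocol and SAP*

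**What the plan says.** - **Endpoint.** Study Endpoints gives the primary thrombotic endpoint as incidence "total & per type e.g. PE, DVT, symptomatic, incidental, proximal, distant etc". Incidental events are therefore one component of the total.
- **Definitions (Efficacy Evaluations).** Symptomatic PE needs symptoms and imaging: "Confirmation of symptomatic PE requires symptoms of PE and one of the following findings". Incidental PE needs only an imaging finding: "Incidental PE with one of the following". For DVT, "Confirmation of incidental DVT requires inconclusive or no- symptoms of DVT and" is followed by an ultrasound finding. Fatal PE has a second limb that needs no scan: "Death not attributed to a documented cause and for which DVT/PE cannot be ruled out".
- **Data source (Study Phases).** "All the data will be gathered from medical records by chart review of the individual patients in a retrospective fashion". The study has no contact with patients.
- **Time points (Study Design).** "In all cases, laboratory and clinical parameters will be collected at 3 time points: at admission/baseline, after one week and at discharge". Thrombotic events are collected over the whole hospital stay. Study Objectives adds that imaging results will be recorded.
- **Associations.** Study Design plans to relate a "panel of laboratory and clinical parameters representing an inflammatory and hemostatic state with VTE and bleeding events and clinical outcomes"; D-dimer heads the list of markers. The Statistical and Analytic Plan also relates type and duration of thromboprophylaxis to the primary outcomes. It uses univariate tests and a logistic model at p < 0.05 and names no imaging variable. It adds that correlations will be discussed with care and serve only to assess hypotheses.

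**The concern.** A silent PE or DVT enters the data only if someone ordered a scan. Under routine care that decision rests with the treating team, and it may depend on the characteristics the study wants to relate to VTE. A raised D-dimer is a plausible reason to scan. So is high perceived thrombotic risk, which the Introduction says also guided dose escalation. If scanning is more frequent at high marker values or in one dose group, more silent events are found there, and an association can appear where none exists.

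At stake is a stated aim of the study: to relate patient profile, markers and thromboprophylaxis approach to thrombotic events. The total incidence is affected too, because its incidental part rises or falls with imaging practice. The exclusion of known or suspected PE or DVT comes with no baseline scan, so it will often be impossible to verify that an incidental finding is new.

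**Working it through.** The documents give no sample size, event rate or imaging rate, so there is no planned figure to reproduce. Every rate below is an assumption.

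**1. Single illustration**

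Inputs, equal in the high and low D-dimer groups: symptomatic VTE 2% of patients, always found; silent VTE 3% of patients, found only if scanned. Scanned: 40% at high D-dimer, 10% at low. The true odds ratio is 1.

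Observed risk = symptomatic + silent × share scanned.
- High: 2% + 3% × 0.40 = 3.2%
- Low: 2% + 3% × 0.10 = 2.3%
- Odds ratio = (0.032/0.968) / (0.023/0.977) = 0.03306 / 0.02354 = 1.40

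**2. Wider range**

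Let s be the symptomatic risk, q the silent prevalence among the remaining patients, and f the share of them scanned. Observed total = s + (1 − s) × q × f.

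With s = 2% and q = 5%:

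| f | Observed total |
|---|---|
| 0% | 2.0% |
| 10% | 0.02 + 0.98 × 0.05 × 0.10 = 2.49% |
| 30% | 3.47% |
| 50% | 4.45% |
| 100% | 6.9% |

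Over s of 1 to 3% and q of 2 to 10%, the fully scanned total is 1.6 times (4.94/3.0) to 10.9 times (10.9/1.0) the total with no asymptomatic scanning.

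Odds ratio with no true association:

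| Scanned, low vs high D-dimer | s = 2%, q = 5% | Range over s and q |
|---|---|---|
| 10% vs 10% | 1.00 | 1.00 |
| 10% vs 30% | (0.0347/0.9653) / (0.0249/0.9751) = 1.41 | 1.13 to 2.04 |
| 10% vs 50% | (0.0445/0.9555) / (0.0249/0.9751) = 1.82 | 1.25 to 3.12 |

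**3. Chance of a false finding**

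This assumes 500 patients per D-dimer group, s = 2%, q = 5%, a two-sided 0.05 test (the plan does not state sidedness) and a normal approximation. The chance of a significant positive association is about 15% at 10% versus 30% scanned and about 40% at 10% versus 50%. The nominal figure in that direction is 2.5%.

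**4. After restriction to symptomatic VTE**

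The term in f drops out. The observed incidence equals s at any scan rate, and the odds ratio is 1.00 under no true association. This holds only if every symptomatic patient is imaged whatever the D-dimer.

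**The case against.** The strongest case on the other side has five parts.

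- **Symptomatic and incidental events are already separate types.** This stands for reporting: a reader can take the symptomatic rate from the primary endpoint. It does not reach the association analyses, which are not limited to a type, and it separates numerators without saying how many patients were imaged.
- **A retrospective study cannot schedule scans.** Correct. A reader might infer that the lack of imaging at the three time points is a defect. It is not; those time points govern laboratory and clinical parameters. The gap is the absence of a rule for unequal scanning.
- **The total does not simply follow scanning.** Also correct. In the first illustration symptomatic events make up 2.0 of 3.2 points (63%) and 2.0 of 2.3 points (87%), and fatal PE can count without a scan. The statement is limited to the incidental component.
- **Correlations are only for hypotheses, and multivariate analysis may be done.** This lowers the stakes. A general caveat does not remove a bias with a direction, and adjustment cannot address scanning unless scan status is available and used.
- **The document is a synopsis and the CRF is not shown.** Imaging results are to be recorded, so suitable fields may exist. What can be said is that the analysis text makes no use of them.

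**Conclusion.** The point holds as a specific gap in a stated analysis, and the change is worth making. Incidental events found only through routine-care scans are part of the thrombotic outcome, and the marker and dose associations neither separate them nor account for imaging. On assumed rates, with no true association, the odds ratio is about 1.4 in the base illustration. It runs from 1.13 to 3.12 over the unequal-scanning scenarios tabulated, and it is 1.00 if scanning is equal.

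Three stronger readings are tempting and not supported:

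- That D-dimer or dose did drive scanning. No section says so. The bias is possible, and its size cannot be derived from the documents.
- That the plan counts never-scanned patients as event-free over an all-patient denominator. That is the natural reading of incidence, but no denominator is stated.
- That all VTE detection depends on scanning in the same way, which would give a much larger distortion. Symptomatic events are prompted by symptoms. If their confirmation did depend on D-dimer to the same degree, a symptomatic endpoint would carry the same bias.

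**What to change.** 1. Make objectively confirmed symptomatic VTE, together with objectively confirmed fatal PE, the main outcome for the marker and dose associations and the lead incidence line. Show unexplained deaths that meet the fatal PE definition on a separate line, since they are unverified.
2. Keep the overall total and the incidental events as descriptive lines.
3. From the charts, record for each patient whether imaging capable of showing PE or DVT was done, its date and its reason (symptoms, laboratory value, other).
4. Report incidental events with the number of patients imaged, and show imaging rates by D-dimer level and by dose group.
5. Label any analysis restricted to imaged patients as exploratory. Imaging may itself depend on the marker, so the restriction can introduce selection bias.

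The cost is fewer events in the lead line and in the association models, some endpoint wording, and a few fields from charts already under review. The bias is reduced, not removed, because symptomatic events also need imaging confirmation; the report should say so.

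### Length of hospital stay has no rule for in-hospital death, and the methods named for continuous outcomes do not separate discharge alive from death

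*Combined protocol and SAP*

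**What the plan says.** Under Study Endpoints, the second secondary endpoint is "Length of hospital stay (days"). No start event, end event or handling of death is given. The Statistical and Analytic Plan sets a general default: "Continuous variables will be reported as mean and standard deviations (SD) and will be analyzed using the *t-test* analysis". For relating patient and disease characteristics to the primary and secondary outcomes it adds ANOVA, "Mann-Whitney U tests* and *t-tests*, according to the data properties", within a list left open to other methods. The Clinical Study Report paragraph adds medians, ranges and quartiles, and sets significance at p below 0.05. The results of correlations "will be used only to assess hypotheses".

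The documents do provide for deaths:
- Data collection includes "Clinical improvement and/or survival during hospitalization".
- Efficacy Evaluations defines fatal PE, including by autopsy or as "Death not attributed to a documented cause and for which DVT/PE cannot be ruled out".
- Safety Evaluations lists "Bleeding contributing to death" as major bleeding.
- The WHO scale scores death as 10.
- The exclusion criterion that concerns dying covers only patients in whom "Progression to death was imminent and inevitable within 24 hours from the admission".

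Other text points to few deaths. The eligibility criteria require signed informed consent, with no proxy or waiver described, and exclude patients admitted to ICU. The Introduction describes the population as having moderate disease.

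**The concern.** A hospital stay can end in discharge alive or in death. A plain count of days treats the two endings alike unless a rule says otherwise. Mann-Whitney, medians and quartiles deal with skewness but do not tell the endings apart.

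This matters because the plan intends to relate thromboprophylaxis approach and patient profile to clinical outcomes. The Introduction says doses are raised according to risk factors, so the groups compared could plausibly differ in mortality. A difference in mean stay would then have no single reading: it could reflect the speed of recovery, the number of deaths, or when deaths happened. The primary endpoints (thrombotic and bleeding events) are not affected.

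**Working it through.** The plan has no figure to reproduce. It states no sample size, expected stay, SD, mortality or timing of death, so every input below is an assumption.

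**1. Shift in the mean.** Let S be survivors' mean stay, D the mean day of death and p the in-hospital mortality. If every patient contributes days to the end of stay, the mean is (1 - p) x S + p x D. For two groups with the same S and D, the difference (higher-mortality minus lower-mortality group) is (p2 - p1) x (D - S). For example, at 5% v 15% with S = 10 and D = 5: 0.10 x (5 - 10) = -0.50 days.

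| Mortality | S | D = 5 | D = 7 | D = 10 | D = 14 |
|---|---|---|---|---|---|
| 5% v 15% | 7 | -0.20 | 0 | +0.30 | +0.70 |
| 5% v 15% | 10 | -0.50 | -0.30 | 0 | +0.40 |
| 5% v 15% | 14 | -0.90 | -0.70 | -0.40 | 0 |
| 2% v 5% | 7 | -0.06 | 0 | +0.09 | +0.21 |
| 2% v 5% | 10 | -0.15 | -0.09 | 0 | +0.12 |
| 2% v 5% | 14 | -0.27 | -0.21 | -0.12 | 0 |

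The sign depends on whether deaths come before or after a typical discharge. With no deaths the shift is zero.

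**2. How often this would mislead.** Simulation: gamma-distributed stays, survivors' mean 10 and SD 5 in both groups, SD of time to death half its mean, 250 per group, 4,000 runs, Welch t-test at two-sided 0.05. Each cell gives the percentage of runs in which the higher-mortality group has the shorter mean and, in brackets, a significantly shorter one.

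| Mortality | D = 5 | D = 7 | D = 10 | D = 14 |
|---|---|---|---|---|
| 5% v 15% | 87.2 (20.2) | 74.5 (9.2) | 49.5 (2.1) | 21.2 (0.4) |
| 2% v 5% | 63.0 (5.5) | 58.9 (3.9) | 49.2 (2.4) | 38.8 (1.1) |

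With equal mortality in both groups the figures are 49.0 to 50.1 (2.1 to 2.8). At 100 per group and D = 5 they are 75.6 (10.4) at 5% v 15% and 58.6 (4.3) at 2% v 5%.

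**3. Changing the test.** In a repeat run with D = 5 and 250 per group, the t-test found a significantly shorter stay in 20.7% of runs (5% v 15%) and 5.6% (2% v 5%). Mann-Whitney found it in 25.8% and 5.9%. Choosing the test by data properties does not remove the problem.

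**4. Masking.** Steps 1 to 3 assume equal stays among survivors. Suppose survivors in the higher-mortality group stay one day longer (11 v 10), with D = 5:
- 5% v 15%: (0.85 x 11 + 0.15 x 5) - (0.95 x 10 + 0.05 x 5) = 10.10 - 9.75 = +0.35 days.
- 2% v 5%: (0.95 x 11 + 0.05 x 5) - (0.98 x 10 + 0.02 x 5) = 10.70 - 9.90 = +0.80 days.

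A true one-day difference among survivors shows as 0.35 or 0.80 days. The higher-mortality group then has the shorter mean in only 23% and 4% of runs.

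**5. The alternative measure.** With S = 10 and SD 5, P(survivor's stay is at most 14 days) = 0.8094. The proportion discharged alive by day 14 is (1 - p) x 0.8094: 79.3% at 2% mortality, 76.9% at 5% and 68.8% at 15%. It does not depend on when deaths occur. These figures only restate the assumed mortality, however. A lower value could mean more deaths or slower recovery, so deaths must be reported beside it.

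**The case against.** The strongest objection is that the problem may never arise. Signed consent is required with no stated route for deceased patients, ICU admissions are excluded, and the population is of moderate severity. Definitions of fatal events classify what might occur; they do not show that deceased patients enter the cohort. This stands, and it is why the point is conditional.

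Second, a reader might infer that the plan counts an early death as a short stay, so that higher mortality would look like a better result. The documents do not support that. No sentence assigns a test specifically to length of stay or says that a death yields a stay value, and the last visit is defined only at discharge. The direction is also not fixed: it reverses when deaths come late, and differing stays among survivors can turn a false difference into a masked one. What the text supports is that no rule is stated.

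Third, deaths are visible elsewhere, through the survival data and the WHO scale, and correlations serve only to assess hypotheses. That limits the harm but does not make the stay comparison itself interpretable.

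Fourth, the open methods list would allow a suitable analysis. It permits one without committing to it, and choosing after seeing the data is weaker than stating the rule now.

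**Conclusion.** The point holds in conditional form. Length of stay has no rule for in-hospital death, and none of the named methods separates discharge alive from death. If deceased patients are enrolled, comparisons by dose or profile mix the two.

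The size rests entirely on assumed inputs. Moderate severity and the ICU exclusion point towards the lower-mortality scenario. There (2% v 5%), across all assumed stays and death timings, the shift runs from -0.27 to +0.21 days. With deaths averaging day 5 and survivors' stays equal at a mean of 10 days, a misleading significant result occurs in 5.5% of runs against about 2.5% by chance. The 5% v 15% scenario shows what a larger mortality gap could do; nothing in the documents suggests it is expected. This is an optional, cheap improvement to one secondary, hypothesis-level result.

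**What to change.** Add one or two sentences to the Statistical and Analytic Plan:
- Analyse time from admission to discharge alive, with in-hospital death as a competing event (cumulative incidence).
- Report the number and cumulative incidence of in-hospital deaths beside it. Without this, the new measure does not by itself separate slower recovery from more deaths.
- Show length of stay among survivors as descriptive only.
- If no deceased patients are enrolled, keep the plain analysis and state that it describes survivors only.

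The cost is slightly more analysis and a summary less familiar than mean days. With few deaths the result will differ little from the plain comparison. The date of death must be available from the chart. The data collection list names no admission, discharge or death date, so its silence is not evidence that the date is missing; a check of the CRF is enough. No new patients or time points are needed.
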